14.3.1.4 Non-measurable evaluable disease

Unidimensionally measurable lesions, masses with margins not clearly defined, lesions with maximal diameter < 1 cm.

14.3.2 Response/Progression Categories

Complete response (CR)

All of the following criteria must be met:

- a. Complete disappearance of all enhancing measurable and non-measurable disease sustained for at least 4 weeks. In the absence of a confirming scan 4 weeks later, this scan will be considered only stable disease.
- b. No new lesions.
- c. All measurable and non-measurable lesions must be assessed using the same techniques as baseline.
- d. Participants must be on no steroids or on physiologic replacement doses only.
- e. Stable or improved non-enhancing (T2/FLAIR) lesions
- f. Stable or improved clinically, for clinical signs and symptoms present at baseline and recorded to be disease related

Participants with non-measurable disease cannot have a complete response. The best response possible is stable disease.

Partial response (PR)

All of the following criteria must be met:

- a. Greater than or equal to 50% decrease compared to baseline in the sum of products of perpendicular diameters of all measurable enhancing lesions sustained for at least 4 weeks. In the absence of a confirming scan 4 weeks later, this scan will be considered only stable disease.
- b. No progression of non-measurable disease.
- c. No new lesions.
- d. All measurable and non-measurable lesions must be assessed using the same techniques as baseline.
- e. The steroid dose at the time of the scan evaluation should be no greater than the dose at time of baseline scan.
- f. Stable or improved non-enhancing (T2/FLAIR) lesions on same or lower dose of corticosteroids compared to baseline scan.

- g. Stable or improved, for clinical signs and symptoms present at baseline and recorded to be disease related clinically.

Participants with non-measurable disease cannot have a partial response. The best response possible is stable disease.

Progressive disease (PD)

The following criterion must be met:

- a. 25% increase in sum of the products of perpendicular diameters of enhancing lesions (over best response or baseline if no decrease) on stable or increasing doses of corticosteroids

and/or one or more of the following:

- b. Significant increase in T2/FLAIR non-enhancing lesion on stable or increasing doses of corticosteroids compared to baseline scan or best response following initiation of therapy, not due to co-morbid events (radiation therapy, demyelination, ischemic injury, infection, seizures, post-operative changes, or other treatment effects).
- c. Any new lesion
- d. Clear clinical deterioration not attributable to other causes apart from the tumor (e.g., seizures, medication side effects, complications of therapy, cerebrovascular events, infection, etc.). The definition of clinical deterioration is left to the discretion of the investigator but it is recommended that a decline in the KPS from 100 or 90 to 70 or less, a decline in KPS of at least 20 from 80 or less, or a decline in KPS from any baseline to 50 or less, for at least 7 days, be considered neurologic deterioration unless attributable to comorbid events or changes in corticosteroid dose. Similarly, a decline in the Eastern cooperative Oncology Group (ECOG) performance scores from 0 or 1 to 2 or 2 to 3 would be considered neurologic deterioration, unless attributable to co-morbid events or changes in corticosteroid dose.
- e. Failure to return for evaluation due to death or deteriorating condition
- f. Patients with non measurable enhancing disease whose lesions have significantly increased in size and become measurable (minimal bidirectional diameter of ≥ 10 mm and visible on at least two axial slices that are preferably, at most, 5 mm apart with 0-mm skip) will also be considered to have experienced progression. The transition from a non measurable lesion to a measurable lesion resulting in progression can theoretically occur with relatively small increases in tumor size (e.g., a 9×9 mm lesion [non measurable] increasing to a 10×11 mm lesion [measurable]). Ideally, the change should be significant (> 5 mm increase in maximal diameter or $\geq 25\%$ increase in sum of the products of perpendicular diameters of enhancing lesions). In general, if there is doubt about whether the lesion has progressed, continued treatment and close follow-up evaluation will help clarify whether there is true progression.

Note that if there is uncertainty regarding whether there is progression, the patient may continue on treatment and remain under close observation (e.g., evaluated at 4-week intervals). If subsequent evaluations suggest that the patient is in fact experiencing progression, then the date of progression should be the time point at which this issue was first raised.

Stable disease (SD)

All of the following criteria must be met:

- a. Does not qualify for CR, PR, or progression.
- b. All measurable and non-measurable sites must be assessed using the same techniques as baseline.
- c. Stable non-enhancing (T2/FLAIR) lesions on same or lower dose of corticosteroids compared to baseline scan. In the event that the corticosteroid dose has been increased, the last scan considered to show stable disease will be the scan obtained when the corticosteroid dose was equivalent to the baseline dose.
- d. Stable clinically.

Unknown response status

Progressive disease has not been documented and one or more measurable or non-measurable lesions have not been assessed.

These RANO Response Criteria are also summarized in [Table 14-4](#):

Table 14-4 Summary of the RANO Response Criteria

	CR	PR	SD	PD#
T1-Gd +	None	≥50% decrease	<50% decrease but ≤ 25% increase	≥25% increase*
T2/FLAIR	Stable or decrease	Stable or decrease	Stable or decrease	Increase*
New Lesion	None	None	None	Present*
Corticosteroids	None	Stable or decrease	Stable or decrease	NA**
Clinical Status	Stable or improve	Stable or improve	Stable or improve	Deterioration*
Requirement for Response	All	All	All	Any*

CR=complete response; PR=partial response; SD=stable disease; PD=progressive disease

*: Progression when this criterion is met **: Increase in corticosteroids alone will not be taken into account in determining progression in the absence of persistent clinical deterioration

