14.3.1.3 Measurable disease

Bidimensionally, contrast-enhancing, measurable lesions with clearly defined margins by CT or MRI scan, with a minimal diameter of 1 cm, and visible on at least 2 axial slices which are preferably at least 5 mm apart with 0 mm skip. If the MRI is performed with thicker slices, the size of the measurable lesion at baseline should be two times the slice thickness. Measurement of tumor around a cyst or surgical cavity should be considered non measurable unless there is a nodular component measuring ≥ 10 mm in diameter. The cystic or surgical cavity itself should not be measured in determining response. If there are too many measurable lesions to measure at each evaluation, the investigator must measure at least the largest two to be followed before a participant is entered on study, with the total measurement representing the sum of products of the perpendicular diameters. A maximum of five lesions should be measured. The remaining

lesions will be considered non-measurable for the purpose of objective response determination. Unless progression is observed, objective response can only be determined when all measurable and non-measurable lesions are assessed.

Patients without measurable disease, such as those who undergo a gross total resection, cannot respond and can only achieve stable disease as their best radiographic outcome.

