14.3.4 Evaluation of Best response

The best overall response is the best response recorded from the start of the treatment until disease progression (taking as reference for progressive disease the smallest measurements recorded since the treatment started). If a response recorded at one scheduled MRI does not persist at the next regular scheduled MRI, the response will still be recorded based on the prior scan, but will be designated as a non-sustained response. If the response is sustained, i.e. still present on the subsequent MRI, it will be recorded as a sustained response, lasting until the time of tumor progression. Participants without measurable disease may only achieve SD or PD as their best “response.”

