2.7.1 Objective Response Rate

Objective response rate (ORR) is defined as the proportion of patients with a best overall response of Complete Response (CR) or Partial Response (PR), as per the RANO criteria.

The ORR analysis will include patients from the FAS who have measurable disease (as per RANO) at their baseline scan. ORR will be reported with 95% confidence interval and response will be listed.

This analysis will be done for all patients in the PPS as well as the FAS in both treatment groups pooled together.

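### Appendix 3 bars CR and PR for anyone with non-measurable disease, contradicting its own response criteria; applied literally, this could make ORR scoring inconsistent and only ever lower it

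*Protocol*

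**What the plan says.** ORR is a secondary efficacy endpoint: the proportion with a best overall response of CR or PR under the RANO criteria, as assessed by the investigator (Protocol Table 3-1 and 10.5.2). The SAP limits the denominator: "The ORR analysis will include patients from the FAS who have measurable disease (as per RANO) at their baseline scan" (SAP 2.7.1). Protocol 10.5.2 does the same. Both repeat the analysis in the PPS.

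The criteria are in Protocol Appendix 3. In 14.3.2, CR and PR are each a list of conditions that must all be met, followed by a closing sentence. For CR it reads "Participants with non-measurable disease cannot have a complete response. The best response possible is stable disease"; for PR it reads "Participants with non-measurable disease cannot have a partial response. The best response possible is stable disease".

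Three kinds of lesion count as non-measurable:

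- lesions with a maximal diameter below 1 cm (14.3.1.4);
- lesions beyond those chosen for measurement, of which there are at most five: the remaining "lesions will be considered non-measurable for the purpose of objective response determination" (14.3.1.3);
- cavity-rim tumor: "Measurement of tumor around a cyst or surgical cavity should be considered non measurable unless there is a nodular component" of at least 10 mm (14.3.1.3).

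**The concern.** The two closing sentences turn on whether a participant has non-measurable disease, not on whether measurable disease is absent. A patient can have both. Taken at their word, the sentences deny a response to a patient whose measurable tumor has shrunk by more than half, or vanished, because a small or unmeasured lesion was also present.

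Such a patient has measurable disease at baseline and so is counted in the ORR denominator. If the sentence is applied, that patient cannot reach the numerator. ORR would then depend partly on how many minor lesions a patient has, on how many lesions the investigator chose to measure, and on how each site reads the sentence.

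**Working it through.** The documents state no expected ORR, target or power for ORR, so there is no figure to reproduce. The check is textual, followed by an illustration of size.

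**Step 1. Compare the closing sentences with the rules around them.**

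| Place in Appendix 3 | What it implies for a patient with both kinds of disease |
|---|---|
| 14.3.2, closing sentences of CR and PR | Response impossible; stable disease at best |
| 14.3.2, CR (a): "Complete disappearance of all enhancing measurable and non-measurable disease sustained for at least 4 weeks" | Response possible; the non-measurable disease must also disappear |
| 14.3.2, PR (b): "No progression of non-measurable disease" | Response possible; the non-measurable disease must not progress |
| 14.3.1.2 | Evaluable for response, because measurable disease is present at baseline |
| 14.3.1.3, last paragraph | Not barred; the bar is on patients without measurable disease |
| 14.3.4: "Participants without measurable disease may only achieve SD or PD as their best" response | Not barred, for the same reason |
| Table 14-4 | No bar appears |

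Under the literal reading PR (b) could never matter, since anyone it applies to is already excluded. The same holds for the non-measurable part of CR (a). The closing sentences are therefore wrong as written. The surrounding text supports limiting them to participants with only non-measurable disease.

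**Step 2. Apply the literal rule to constructed records.** Assume in each case that the change is confirmed at 4 weeks, there are no new lesions, and T2/FLAIR and clinical status are stable.

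- Record A. Baseline: a 30 × 20 mm lesion (600 mm²) and a separate 8 × 6 mm lesion. The larger falls to 18 × 12 mm (216 mm²), a change of (216 − 600)/600 = −64%. The smaller does not progress and the steroid dose is unchanged. PR (a) to (g) are met, but the closing sentence gives stable disease. Table 14-4 reserves stable disease for a decrease of less than 50%, so the literal label does not fit there either.
- Record B. Same baseline; both lesions disappear and the patient is off steroids. CR (a) to (f) are met, but the closing sentence gives stable disease.
- Record C. Seven lesions, five measured; all shrink by more than 50% and the steroid dose is unchanged. The two unmeasured lesions count as non-measurable, so the closing sentence gives stable disease.

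**Step 3. Direction.** These patients remain in the denominator because they have measurable disease at baseline. The sentences can remove a CR or PR but cannot create one, so any error lowers ORR.

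**Step 4. Illustrative size.** Let p be the true ORR and m the share of true responders who both have such a lesion and are scored literally. Then reported ORR = p × (1 − m). Both p and m are assumptions; neither is in the documents.

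| p | m = 0 | m = 10% | m = 25% | m = 50% |
|---|---|---|---|---|
| 20% | 20% | 18% | 15% | 10% |
| 30% | 30% | 27% | 22.5% | 15% |

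In counts, use the planned 24 (PPS) and 34 (FAS) from Protocol 10.4.1. These are upper bounds for the ORR denominator, because patients without measurable disease drop out. The starting count of 5 responders is assumed. Intervals are exact (Clopper-Pearson) 95%.

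| Denominator | 5 responders | 4 responders (one rescored) |
|---|---|---|
| 24 | 20.8% (7.1 to 42.2) | 16.7% (4.7 to 37.4) |
| 34 | 14.7% (5.0 to 31.1) | 11.8% (3.3 to 27.5) |

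Two rescored responders of 24 would give 3/24 = 12.5% (2.7 to 32.4).

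**Step 5. Reach.** The closing sentences do not appear in the PD definition. The reference for progression is the smallest measurement since treatment started (14.3.4), which is the same whether the scan is labelled PR or SD. PFS6 and its success rule (Protocol 10.4.2, SAP 2.5.2) are therefore not affected.

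**The case against.** The strongest reply is that the appendix already resolves the matter. Sections 14.3.1.3 and 14.3.4 state the rule correctly, 14.3.1.2 sets evaluability by the presence of measurable disease, and Table 14-4 contains no bar. Directly after the surplus-lesion sentence, 14.3.1.3 says that, absent progression, response can be determined only once both measurable and non-measurable lesions have been assessed. That plainly expects the two to coexist in a patient whose response is being judged. On this view the closing sentences use non-measurable disease as shorthand for a category of patient, and an experienced investigator would read them so.

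Much of this stands, and it limits the point. A reader might infer that true responders are being scored as stable disease and that ORR is biased downward. The documents do not support that. Response is judged by the investigator and entered on the overall response eCRF, and no section directs a programmed derivation from these sentences. Misscoring happens only if someone applies them against their neighbours.

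A reader might also infer that many patients are exposed, because tissue from a prior surgery is normally required and cavity-rim tumor would then be common. The documents give no frequency. Where the rim itself has a nodule of at least 10 mm, the exception in 14.3.1.3 applies, so only rim tumor separate from the measurable lesion is caught.

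It is also fair that the consequence is modest. ORR is descriptive, has no success rule or power calculation, and the one-responder shifts above sit inside wide, overlapping intervals.

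The reply does not remove the contradiction. Each closing sentence follows a complete list of conditions and reads as an override. SAP 2.7.1 refers only to the RANO criteria and does not settle the reading. In a multicenter study with investigator assessment, two sites could score the same scans PR and SD and both cite Appendix 3.

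**Conclusion.** The closing sentences of the CR and PR definitions are wrong as written and contradict the rest of Appendix 3. The consequence is a risk of inconsistent scoring between sites, in which any error can only lower ORR; it is not a demonstrated bias.

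The size is unknown. It is zero if sites follow 14.3.1.3 and 14.3.4. Otherwise it depends on how many true responders have coexisting non-measurable disease and how many of those are scored literally. The documents give neither, so the percentages above are illustrations and not expected effects. With at most 24 or 34 patients, one rescored responder costs 1/24 = 4.2 or 1/34 = 2.9 percentage points. The point warrants correction because ORR is a named secondary efficacy endpoint and the change is small. It has no bearing on the primary conclusion.

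**What to change.** In Protocol 14.3.2, replace both closing sentences with: *Participants with only non-measurable disease (no measurable disease at baseline) cannot have a complete [partial] response; the best response possible is stable disease.* This matches 14.3.1.3 and 14.3.4.

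In SAP 2.7.1, add: *Non-measurable lesions present alongside measurable disease do not preclude CR or PR, provided CR criterion (a) or PR criterion (b) and the remaining criteria are met.*

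Before database lock, query any overall response of stable disease that was entered solely because a non-measurable lesion was present.

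The cost is a clarification in two protocol sentences, one SAP sentence and, if any such entries exist, a few data queries. No new assessments are needed and no other endpoint changes.

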14.3.3 Methods for Evaluation of Measurable Disease

All measurements should be taken and recorded in metric notation, using a ruler, calipers, or digital measurement tool. All baseline evaluations should be performed as closely as possible to the beginning of treatment and never more than 14 days before the beginning of the treatment.

The same method of assessment and the same technique should be used to characterize each identified and reported lesion at baseline and during follow-up.

14.3.4 Evaluation of Best response

The best overall response is the best response recorded from the start of the treatment until disease progression (taking as reference for progressive disease the smallest measurements recorded since the treatment started). If a response recorded at one scheduled MRI does not persist at the next regular scheduled MRI, the response will still be recorded based on the prior scan, but will be designated as a non-sustained response. If the response is sustained, i.e. still present on the subsequent MRI, it will be recorded as a sustained response, lasting until the time of tumor progression. Participants without measurable disease may only achieve SD or PD as their best “response.”

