7.2 Assessment types

7.2.1 Efficacy assessments

Tumor response and progression will be assessed by the Investigator, using the Response Assessment in Neuro-Oncology (RANO) Working Group ([Wen et al. 2010](#)) as detailed in [Appendix 3](#).

Each patient will be evaluated for all potential sites of tumor lesions at Screening and every 8 weeks after starting study treatment until disease progression.

On-study tumor assessments have a ± 7 day window, except for the first post-baseline tumor assessment and for confirmatory scans (4 weeks +7 day window only). The first post-baseline tumor assessment should be performed on day 1 of cycle 3 (+7 day window permitted) after starting treatment. There will be a tumor assessment at the End of Treatment (+ 7 days) if the patient discontinues for any reason other than disease progression and the last tumor assessment has been performed > 28 days prior to this day.

For group 1, the baseline scan must occur within 28 days of treatment initiation. For group 2, patients undergoing surgery, per standard of care, a MRI should be performed within 72 hours after surgery ([Wen et al. 2010](#)). This scan can function as the baseline scan if BGJ398 therapy is initiated within four weeks of surgery. If BGJ398 is initiated after 4 weeks following surgery, a baseline scan must be performed within 7 days of starting BGJ398. Subsequent post baseline scans will be performed as described above. For group 2 patients who do not undergo surgery the baseline scan will be defined as per group 1.

Note: in case a patient cannot tolerate MRI, the patient may still participate in the study following discussion between Novartis and the investigator. In this case, all efficacy assessments will be made by CT scans for that patient. Efficacy assessments should be performed by using the same technique throughout the study for each patient.

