7.2.2.6 Radiological examinations

7.2.2.6.1 MRI scan (or CT if patient is unable to undergo MRI).

Please refer to details in [Section 7.2.1](#) and [Appendix 3](#). The same modality (MRI/CT) must be used throughout the study

First post baseline scan occurs cycle 3 day 1; subsequent scans occur every 8 weeks until unacceptable toxicity or disease progression, whichever occurs first.

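### Protocol 14.3.2 and 14.3.4 can class the same unconfirmed, short-lived response as stable disease or as a response, and neither ORR definition says which rule governs.

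*Protocol*

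**What the plan says.** Protocol 14.3.2 makes duration part of the definition of response. A PR requires the 50% decrease in the "sum of products of perpendicular diameters of all measurable enhancing lesions sustained for at least 4 weeks", and the same minimum duration applies to CR. Under both categories it adds: "In the absence of a confirming scan 4 weeks later, this scan will be considered only stable disease".

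Protocol 14.3.4 then defines the summary measure: "The best overall response is the best response recorded from the start of the treatment until disease progression". For a response that is seen once and is gone at the following 8-weekly scan, it says that "the response will still be recorded based on the prior scan, but will be designated as a non-sustained response". A response still present on the subsequent MRI is called sustained. The section does not mention a confirming scan.

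On timing, Protocol 7.2.2.6 states: "First post baseline scan occurs cycle 3 day 1; subsequent scans occur every 8 weeks". Protocol 7.2.1 and SAP 2.7 also refer to confirmatory scans at 4 weeks, with a window of +7 days.

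SAP 2.7.1 defines ORR as the "proportion of patients with a best overall response of Complete Response (CR) or Partial Response (PR), as per the RANO criteria". Protocol 10.5.2 uses the same definition and points to Appendix 3. Neither says whether confirmation is required or whether a non-sustained response counts.

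**The concern.** ORR rests on best overall response, and best overall response rests on an appendix with two rules that do not always give the same answer. A programmer working from 14.3.2 would code an unconfirmed, short-lived PR as stable disease. A programmer working from 14.3.4 would code it as a PR. Other parts of the documents do not settle it. The summary in Table 14-4 has no confirmation row. The response categories listed for the overall response eCRF (CR, PR, PD, SD, NA) have no entry for confirmed or non-sustained. SAP 5.1.2.1 gives date rules for tumor assessments but no derivation of best overall response.

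At stake is a named secondary efficacy endpoint, assessed by the investigator in an open-label, single-agent trial. Counting unconfirmed responses can only raise it.

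**Working it through.** The documents give no target, power or expected value for ORR, so there is no stated figure to reproduce. The check sets the two rules side by side and then sizes one discordant patient.

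**Scan calendar.** With 28-day cycles, Cycle 3 Day 1 is day 2 × 28 + 1 = 57. A confirmatory scan 4 weeks later falls on day 57 + 28 = 85, or up to day 92 with the +7-day window. The next regular scan is due on day 57 + 56 = 113, ±7 days, so day 106 to 120. If the first scan is as late as allowed (day 64) and the next as early as allowed (day 106), with scan dates counted from the start of treatment, the gap is 106 − 64 = 42 days, or 6 weeks. A response still present at the next regular scan has therefore been seen at least 4 weeks apart whenever the windows are kept.

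**Cases.** Take a PR first seen at Cycle 3 Day 1.

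| 4-week scan | Next regular scan | 14.3.2 | 14.3.4, read literally | Agree? |
|---|---|---|---|---|
| Confirms PR | PR present | PR | PR, sustained | Yes |
| Confirms PR | PR lost | PR | PR, non-sustained | Yes |
| Not done | PR present | PR (at least 4 weeks met) | PR, sustained | Yes |
| Not done | PR lost | SD | PR, non-sustained | **No** |
| Shows PR lost | PR lost | SD | PR, non-sustained | **No** |

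The third row takes the regular scan as the confirming scan. That fits the 14.3.2 criterion of at least 4 weeks, although the sentence on the missing confirming scan could be read more narrowly.

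**Size of one discordant patient.** The shift in ORR is 1/n. The denominator is the number of patients with measurable disease at baseline, which is not given. The planned FAS of 34 and PPS of 24 (Protocol 10.4.1) are upper limits, so the shifts at those sizes are lower limits for each set.

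- n = 34: 1/34 = 2.9 points
- n = 24: 1/24 = 4.2 points
- n = 20 (assumed): 1/20 = 5.0 points
- n = 15 (assumed): 1/15 = 6.7 points

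**Illustration.** Assume 2 confirmed responders and 2 discordant ones. The intervals are exact (Clopper-Pearson) 95% intervals, also an assumption, because the interval method is not stated.

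| n | 14.3.2 rule | 14.3.4 rule |
|---|---|---|
| 24 | 2/24 = 8.3% (1.0 to 27.0) | 4/24 = 16.7% (4.7 to 37.4) |
| 34 | 2/34 = 5.9% (0.7 to 19.7) | 4/34 = 11.8% (3.3 to 27.5) |

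With no discordant patients the two rules give the same ORR.

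**The case against.** The strongest reply is that the sections can be read together. Section 14.3.2 defines CR and PR by criteria that must all be met, and duration of at least 4 weeks is one of them. Section 14.3.4 follows and does not redefine either category, so a response there may mean one already confirmed. The calendar fits: a PR at week 8, confirmed at week 12 and lost at week 16, would be non-sustained and still a response. The reference to the next regular MRI may be there to separate the 8-weekly scan from the confirmatory one. ORR is also tied to RANO as set out in Appendix 3, where the category definitions carry the confirmation requirement.

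This reading is possible, and it may be what was intended. It is not stated. Section 14.3.4 defines sustained by the subsequent MRI alone and takes the best response recorded without condition, so its literal text also covers a response that was never confirmed. The need for a stated rule stands.

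Three stronger readings may tempt a reader, and the documents do not support them.

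- *That the rules agree only if a 4-week scan was done.* Doing the scan is neither necessary nor sufficient, as the third and fifth rows of the case table show. What matters is confirmation.
- *That the plan makes no provision for confirmatory scans because Table 7-1 does not list one.* Protocol 7.1, Protocol 7.2.1 and SAP 2.7 all provide for them, and a scan that depends on an observed response need not have a fixed visit column. The omission only makes a missed scan more plausible.
- *That the rule would be chosen after the data are seen.* SAP Section 1 says that the decisions on the final analysis defined in the SAP were made before database lock. It refers to table shells that are not among the documents. What can be said is that these two documents do not record the choice.

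**Conclusion.** The point holds as an unresolved conflict with a limited reach. It affects responses that are not confirmed at 4 weeks and are gone by the next regular scan; elsewhere the two rules agree. Each such patient changes ORR by about 2.9 points at n=34 and 4.2 points at n=24, and by more if fewer patients have measurable disease. How many such patients there would be is unknown, and the responder counts in the illustration are assumed. The illustrated intervals overlap widely.

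A reader might infer that the trial's conclusion is at risk. It is not: ORR has no power calculation or decision threshold, and the success rule in Protocol 10.4.2 and SAP 2.5.2 uses PFS6 alone. The matter deserves correction because it can change a reported secondary endpoint and the remedy is small.

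**What to change.** State in SAP 2.7.1 that a CR or PR counts in ORR only if it is confirmed by a scan at least 4 weeks later. This is the sponsor's own criterion in Protocol 14.3.2, and a response still present at the next 8-weekly scan also meets it. Count unconfirmed responses as stable disease for ORR and list them separately, so that the effect of the rule can be seen.

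Align Protocol 14.3.4 with this by limiting the non-sustained label to confirmed responses that are later lost.

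The cost is about one sentence in each document. No new data or further scheduled scans are needed. ORR may be slightly lower than if unconfirmed responses were counted.
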